### **3.5 Discontinuation of Subjects following any Treatment with Study Drug**

Subjects who discontinue treatment with investigational product during the Double-Blind Treatment Period (Day 1 - Week 24) must be assessed for all efficacy measures and for safety at the originally scheduled Week 24 (Day 169 from baseline) time-point (see Post-Study Drug Efficacy Visit - [Table 5.1-4](#)).

All subjects who discontinue study drug at any time throughout the study, require visits to assess safety and immunogenicity at Day 85 and Day 169 after the last dose of study drug (see [Table 5.1-7](#)). For subjects who discontinue during the Double-Blind Period, if either the Day 85 or Day 169 visit falls within  $\pm 14$  days of the Week 24 Post-Study Drug Efficacy Visit ([Table 5.1-4](#)), only perform immunogenicity and pharmacokinetic blood samples ([Table 5.1-7](#)) along with the Post-Study Drug Efficacy Visit.

The only exception to this requirement is when a subject withdraws consent for all study procedures including post-treatment study follow-up or loses the ability to consent freely (ie, is imprisoned or involuntarily incarcerated for the treatment of either a psychiatric or physical illness).

Subjects **MUST** discontinue investigational product (and non-investigational product at the discretion of the investigator) for any of the following reasons:

- Subject's request to stop study treatment
- Subject withdraws consent
- Any clinical adverse event (AE), laboratory abnormality or intercurrent illness which, in the opinion of the investigator, indicates that continued participation in the study is not in the best interest of the subject
- Pregnancy (see additional instruction below)
- Termination of the study by Bristol-Myers Squibb (BMS)
- Loss of ability to freely provide consent through imprisonment or involuntarily incarceration for treatment of either a psychiatric or physical (e.g., infectious disease) illness
- Use of prohibited medication
- Subjects who fail rescue therapy, as judged by the investigator, between Wk 12 and Wk 24
- Subjects who, during the course of the study, require mechanical breathing assistance (ventilator) due to myositis, ILD, or another pulmonary cause. Temporary mechanical breathing assistance during a procedure or elective surgery is permitted.
- Missed Doses
  - Missed 4 or more doses of abatacept/placebo for any reason during the first 24 weeks (Double-Blind Period)

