  - Missed 3 or more consecutive doses of abatacept/placebo for any reason during the first 24 weeks (Double-Blind Period)
  - Missed 6 or more doses of abatacept for any reason between Week 24 and Week 52 (Open-Label Period)
  - Missed 5 or more consecutive doses of abatacept for any reason between Week 24 and Week 52 (Open-Label Period) or Week 76 (for subjects randomized in Japan)
- Significant non-compliance with protocol (i.e., procedures, assessments, medication, etc.). The investigator should discuss such issues with the BMS Medical Monitor.
- Participation in another clinical trial with an investigational product.

In the case of pregnancy, the investigator must immediately notify the Sponsor or designee of this event. In most cases, the study drug will be permanently discontinued in an appropriate manner. Please contact the Sponsor or designee within 24 hours of awareness of the pregnancy. If the investigator determines a possible favorable benefit/risk ratio that warrants continuation of study drug, a discussion between the investigator and the Sponsor or designee must occur.

If study drug is discontinued prior to the subject's completion of the study, the reason for the discontinuation must be documented in the subject's medical records and entered on the appropriate case report form (CRF) page.

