##### **4.5.1 Abatacept Treatment**

Abatacept (125 mg) or matching placebo will be administered subcutaneously (SC) once per week. See [Section 5.1.1.1](#) for dosing windows. On Day 1, subjects and/or personal caregivers will be trained in self-administration of SC injections using pre-filled syringes. Administration of abatacept may be performed by the physician or medical staff at the study site for training purpose through Week 4 if needed. All subsequent injections will be self-administered or administered by a personal caregiver. Medical staff can act as a caregiver only when the subject cannot self-administer and does not have access to a personal caregiver. Training should be performed by investigational site personnel that are considered qualified trainers by the Investigator. Subjects or their caregivers will be trained using instructions that will be provided by BMS or designee.

The last dose of SC abatacept/placebo for the Double-Blind Period will be administered in Week 23 while the last dose of SC abatacept for the Open-Label Period will be administered in Week 51. For subjects randomized from Japan, the last dose of SC abatacept in the Open Label Period will be at Week 75. Also, for subjects (all countries except the U.S. and the Czech Republic) participating in the long term open label extension period, the last dose of SC abatacept will be at Day 1086.

Injections sites may include the upper arms (outside area), thigh, or abdomen. When possible, injection sites and/or sides of the body should be rotated every week. The upper arm injection site should be used only by caregivers and not for self-administration.

To ensure compliance and to monitor technique “office visit” SC injections should be administered in the presence of a qualified investigational staff.

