6.3 Populations for Analyses

Efficacy endpoints will be summarized according to the Intent-to-Treat (ITT) population and safety endpoints will be summarized according to the as-treated analysis population. These populations are described briefly below along with other populations.

- **Intent-to-Treat Analysis Population:**

The Intent-to-Treat (ITT) analysis Population is defined to include all subjects randomized into the study for whom Case Report Form (CRF) data indicate that at least one dose of study medication (abatacept or placebo) is administered during the double-blind period.

All subjects who are randomized but never received study medication are to be excluded. Given the blinded nature of this study, it is reasonable to assume that subjects who discontinue prior to the receipt of study medication do so for reasons unrelated to study medication. Subjects are grouped according to the treatments to which they are randomized by IXRS.

ITT analysis population is also referred to as “All Randomized and Treated Subjects”.

- **As-Treated Analysis Population:**

The As-Treated analysis population contains all subjects for whom CRF data indicate that at least one dose of study medication was administered during double-blind period.

Subjects are grouped according to the treatments to which they are randomized, except in cases where information is available, which indicates that a subject receives a different treatment for the entire course of double-blind period. In this case, the subject will be presented by the treatment they actually received.

The As-Treated analysis population will also be referred as “All Treated Subjects”.

- **Per-Protocol Analysis Population:**

The Per-Protocol analysis population is defined as a subset of the ITT analysis population which excludes subjects who have relevant protocol deviations during the double-blind study period. Relevant protocol deviations are those protocol deviations that might affect the primary efficacy endpoint of the study. A programmable list of relevant protocol deviation criteria is included in [APPENDIX 1](#).

The analysis of the primary efficacy endpoint will be repeated in the Per-Protocol analysis population. The Per-Protocol analysis population will exclude subjects with at least 1 relevant protocol deviation.

- **Open-Label Treated Analysis Population:**

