APPENDIX 1 RELEVANT PROTOCOL DEVIATIONS

Pre-randomization

- Myositis Activity:
 - Screening MMT-8 score of 140 or more.
 - Failure to document criteria for currently active IIM or obtain approval from adjudication committee.
 - Diagnosis of Inclusion Body Myositis.
- Medication/Procedure/Other:
 - Use of rituximab within 3 months.
 - Use of immune globulin within 6 weeks.
 - Discontinuation of prohibited medication within 2 weeks.

Post-randomization

- Medication/Procedure:
 - Use at randomization of more than 1 of the allowable immunosuppressant's drugs in the Double-Blind period.
 - Use of corticosteroids above prednisone $\geq 35\text{mg/day}$ (or prednisone equivalent) for > 3 weeks or within 2 weeks of Day 169.
 - Increase of 5 mg or more per day or initiation of more than 10 mg per day of prednisone (or prednisone equivalent) that is unrelated to management of an AE or permitted rescue therapy.
 - All prohibited medication not discontinued at least 2 weeks prior to randomization with the exception of immune globulin (3 months), rituximab (6 months) and d-penicillamine (3 months). Prohibited medication in this context refers to immunomodulatory medications for the treatment of IIM which are not included as immunosuppressant medications. The following list includes examples of specific prohibited medications:
 - ◆ Adrenal Corticotrophic Hormone (ACTH), including analogues.
 - ◆ Sirolimus.
 - ◆ Everolimus.
 - ◆ Mizoribine.
 - ◆ Tofacitinib or other JAK inhibitor.
 - All investigational or approved biologic DMARD therapies other than abatacept (including but not limited to tocilizumab, adalimumab, golimumab, certolizumab, etanercept, infliximab, anakinra, rituximab, etc.).
 - Use of any investigational drug other than study medication.
- Study conduct:
 - Subject missed more than 6 consecutive doses of study medication (abatacept or placebo) during the Double-Blind period or missed more than 4 consecutive scheduled doses of study medication (abatacept or placebo) between Day 141 and Day 169.

Covid-19 Related Deviations

- Unable to attend both Day 141 and Day 169 assessments due to travel/other restrictions.
- For missed doses due to Covid-19 the same rule to define those as a relevant protocol deviation applies as under study conduct above.

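### The per-protocol missed-dose criterion in SAP Appendix 1 counts only consecutive misses and has no limb for total missed doses, although Protocol 3.5 limits both

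*SAP*

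**What the plan says.** Protocol 3.5 lists two separate missed-dose conditions under which study drug must stop in the Double-Blind Period:

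- a total: "Missed 4 or more doses of abatacept/placebo for any reason during the first 24 weeks (Double-Blind Period");
- a run: "Missed 3 or more consecutive doses of abatacept/placebo for any reason during the first 24 weeks (Double-Blind Period").

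SAP Appendix 1, under study conduct, has one missed-dose criterion with two limbs, both defined by runs. The whole-period limb is "Subject missed more than 6 consecutive doses of study medication (abatacept or placebo) during the Double-Blind period". The alternative limb looks only at the last weeks and applies to a subject who "missed more than 4 consecutive scheduled doses of study medication (abatacept or placebo) between Day 141 and Day 169". Missed doses caused by the pandemic are treated alike: "For missed doses due to Covid-19 the same rule to define those as a relevant protocol deviation applies as under study conduct above". No total and no percentage compliance appears in the list, and neither does a breach of Protocol 3.5.

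The list decides membership. SAP 6.3 states: "The Per-Protocol analysis population will exclude subjects with at least 1 relevant protocol deviation". SAP 6.3 and 7.5 then repeat the primary efficacy analysis in that set. Protocol 8.2 made the repeat conditional on more than 10% of either group having relevant deviations; the SAP performs it regardless.

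**The concern.** The protocol treats accumulated misses as a problem in their own right, separate from a gap in dosing. Appendix 1 keeps the second idea, at a looser cut-off, and drops the first. Misses that are frequent but scattered are thus invisible to the per-protocol definition, however many there are.

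A deviation list matters most when a protocol rule was not followed. A subject who passed the total limit and was kept on drug is the kind of deviator that a per-protocol set is meant to remove. If such subjects stay in, the set is not adherent in the sense a reader will assume. If response depends on exposure, the repeat analysis is also diluted toward no difference.

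**Working it through.** The plan gives no figure on this point to reproduce, so the check is a count of doses.

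**Inputs**
- Frequency: "Abatacept (125 mg) or matching placebo will be administered subcutaneously (SC) once per week" (Protocol 4.5.1).
- Last blinded dose: "The last dose of SC abatacept/placebo for the Double-Blind Period will be administered in Week 23" (Protocol 4.5.1).
- Day 1 is the day of the first dose (SAP 8.5), so no misses precede it.
- Schedule: Weeks 0 to 23, that is Days 1, 8, ..., 1 + 7 × 23 = 162, which makes 24 doses.

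**Patterns tested against both documents**

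| Weeks dosed | Taken | Missed | Longest run of misses | Protocol total (4) | Protocol run (3) | Flagged by Appendix 1 |
|---|---|---|---|---|---|---|
| 0, 2, 4, ..., 22 | 12 | 12 | 1 | reached | not reached | no |
| 0, 4, 8, 12, 16, 20 (office visits only) | 6 | 18 | 3 | reached | reached | no |
| 0, 7, 14, 21 | 4 | 20 | 6 | reached | reached | no |

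The first row is the most informative. Only the protocol's total limit catches it, and that is the limit with no counterpart in Appendix 1. The 12 misses are 12 / 4 = 3 times the limit.

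**The extreme.** If k doses are taken, including Day 1, there are at most k runs of misses, each of at most 6. The schedule can then hold at most k + 6k = 7k doses. Since 7 × 3 = 21 < 24 and 7 × 4 = 28 ≥ 24, the minimum is 4 of 24 (17%). Full enumeration agrees: no pattern with 3 or fewer doses escapes, and 35 of the 1,771 four-dose patterns do. The minimum is also 4 with 23 or 25 scheduled doses.

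**The late limb is no backstop.** Four scheduled doses fall between Day 141 and Day 169 (Days 141, 148, 155 and 162). More than 4 consecutive misses cannot occur there unless Day 169 is counted as a fifth dose. Even then, 4 of the four-dose patterns escape.

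**Scattered misses in general (illustration only).** Assume that each of the 23 doses after Day 1 is missed independently with probability q. The documents do not give q.

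| q | Reaches the protocol total of 4 | Has a run of 7 or more |
|---|---|---|
| 0.2 | 70% | 0.02% |
| 0.3 | 95% | 0.3% |
| 0.5 | over 99.9% | 7% |

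**With a total limb set at the protocol's own count**, an unflagged subject could miss at most 3 doses and would have taken at least 24 − 3 = 21 of 24.

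**The case against.** *Protocol 3.5 already stops these subjects.* It says they must stop, and Protocol 4.7 adds reminder calls, diary cards and inspection of sharps containers. A reader might infer from the arithmetic that the per-protocol set will contain largely undosed subjects. The documents do not support that: the 4-of-24 subject would have to be kept on drug through 20 misses, and no frequency is given. What remains is narrower. The SAP's own threshold of more than 6 in a row has work to do among subjects still on drug only if Protocol 3.5 was not followed, so the list already allows for that case. It covers it for runs and not for totals.

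*A looser cut-off is a legitimate choice.* This stands. Protocol 8.2 leaves the list to the SAP, and relevant deviations are those that might affect the primary endpoint, not every breach. Appendix 1 is looser elsewhere: screening MMT-8 of 140 or more against an entry limit of 135, and a pre-randomization rituximab item of 3 months against 6 in the exclusion criteria (although a later Appendix 1 item cites 6). So the run length of 6 set against the protocol's 3 is not in itself an error. Those items relax a cut-off on the same quantity, however, whereas total misses are left out altogether.

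*Covid-19 misses are handled elsewhere.* In part. SAP 7.2 reports a case-by-case review that covered receipt of medication, and it excludes Covid-19 deviations that could affect the primary endpoint. A reader should not infer that these misses go unexamined. The Appendix 1 rule for them still has no total.

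*Part of the SAP is redacted.* Text after SAP 7.4.2 is blacked out and may include a compliance summary like the one in SAP 11.5.3. Such a summary would not alter the Appendix 1 list, which is legible.

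**Conclusion.** The gap is real and modest. As written, Appendix 1 never flags scattered misses, so a subject who took half of the blinded doses counts as per protocol; the permitted but unlikely extreme is 4 of 24.

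The effect is confined to the per-protocol repeat of the primary analysis. A reader might infer that the trial's main conclusion is at risk. It is not: the primary and secondary analyses use the ITT population, and the testing order in SAP 7.5.1 starts from the primary endpoint without reference to the per-protocol result.

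Dilution toward no difference assumes that response depends on exposure and that some subjects past the total limit were kept on drug. The documents quantify neither. The dose counts assume 24 scheduled doses with the first always given.

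**What to change.** Before unblinding, by which time SAP 7.2 requires relevant deviations to be identified, reconcile Appendix 1 with Protocol 3.5:

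1. Add a limb for total missed doses in the Double-Blind Period, counted from the dosing CRF. State the count and, if it is looser than Protocol 3.5, the tolerance and the reason.
2. Apply it whether or not the site discontinued the subject. If the limb covered only subjects kept on drug, membership would turn on a post-randomization site decision. A subject stopped after 4 misses could stay in as an imputed non-responder (SAP 7.5.2), while one with the same misses who continued and responded would be removed.
3. State whether doses not given after discontinuation count as missed. Appendix 1 is silent; SAP 11.5.3 excludes them from the extension-period compliance summary. It matters: if they count, a subject whose last dose was at Week 16 has 7 remaining (Weeks 17 to 23) and already meets the present run rule. With a total limb of 4, a last dose at Week 19 is enough (Weeks 20 to 23).
4. Apply the same limb to Covid-19 missed doses, alongside the case-by-case exclusion in SAP 7.2.

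The cost is one SAP line, a count from data already collected (SAP 7.4.1.1 counts injections from the CRF), and possibly a slightly smaller per-protocol set. Only the analysis set changes; the protocol's stopping rule is untouched.

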#### **4.5 Selection and Timing of Dose for Each Subject**

On “Office Visit” days, study medication should be administered AFTER all assessments, including blood draws for assessment of immunogenicity and drug concentrations.

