**Table 5.1-2: Study Evaluations - Double-Blind Period (IM101611)**

Study Day a	Day 1	Day 29	Day 57	Day 85	Day 113	Day 141	Day 169	
Procedure	Randomization	Wk 4/ Mo 1	Wk 8	Wk 12/ Mo 3 b	Wk 16	Wk 20	Wk 24 / Mo 6 or DB ET c	Notes
Study Administration								
Confirm Inclusion/Exclusion Criteria	X							
Call IVRS	X	X	X	X	X	X		
Train subjects how to self-inject and how to fill in diary cards	X							
Dispense diary cards	X	X	X	X	X	X		
Collect and review diary cards		X	X	X	X	X	X	
Dosing of weekly abatacept/placebo	X	X	X	X	X	X		Must be administered weekly between visits. See Section 4.5 No dose administered at the Early Termination visit
Reconciliation of abatacept/placebo		X	X	X	X	X	X	
Dispense Study Drug	X	X	X	X	X	X		
Dispense Actigraphy device and train subjects on use	X							
Safety Assessments								
Vital Signs	X	X	X	X	X	X	X	
Weight				X			X	
Targeted Physical Examination	X			X			X	
Adverse Events Monitoring	X	X	X	X	X	X	X	

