**Table 5.1-3: Study Evaluations - Open-Label Period (IM101611)**

Study Day a	Day 169 b	Day 197	Day 225	Day 253	Day 281	Day 309	Day 337	Day 365	
Procedure		Wk 28	Wk 32 (Phone)	Wk 36/ Mo 9	Wk 40 (Phone)	Wk 44	Wk 48 (Phone)	Wk 52 Mo 12 or OL ET	Notes
Study Administration									
Call IVRS	X	X		X		X		X	
Dispense diary cards	X	X		X		X			
Collect and review diary cards		X		X		X		X	
Dosing of weekly abatacept	X	X	X	X	X	X	X	X	Must be administered weekly between visits. See Section 4.5 No dose administered at the Early Termination visit
Reconciliation of abatacept		X		X		X		X	
Dispense urine pregnancy kits for WOCBP		X		X		X			For home use every 4 weeks
Dispense Study Drug	X	X		X		X			
Safety Assessments									
Vital Signs		X		X		X		X	
Weight				X				X	
Targeted Physical Examination				X				X	
Adverse Events Monitoring		X	X	X	X	X	X	X	
		■	■	■	■	■	■	■	

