#### **5.1.1.1 Study Drug Administration Windows**

SC injections of study medication may be administered  $\pm 3$  days of the target day. Subjects who miss the dose window should skip the SC injection and wait until the next targeted administration day.

If abnormal laboratory test results or clinical AEs indicate toxicity that, in the judgment of the investigator, could place the subjects at risk, study medication administration should be withheld. Subjects may receive further study medication only if resolution of the AE or abnormal laboratory finding is documented or, at a minimum, the subject's status returns to what it was at baseline. The investigator can contact the BMS Study Medical Monitor to discuss as needed.

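### SAP Appendix 1 needs at least five consecutive missed doses between Day 141 and Day 169, but only four blinded doses are scheduled there

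*SAP*

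**What the plan says.** SAP Appendix 1, under Study conduct, gives two missed-dose criteria joined by *or*. The first is more than six consecutive doses missed at any time in the double-blind period. The second is that the subject "missed more than 4 consecutive scheduled doses of study medication (abatacept or placebo) between Day 141 and Day 169". The Covid-19 part of the appendix applies the same rule to doses missed because of Covid-19. SAP 6.3 removes any subject with one or more relevant deviations from the per-protocol set and repeats the primary analysis in that set without further condition.

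The dosing schedule is in the protocol:

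- Section 4.5.1 sets weekly dosing and says: "The last dose of SC abatacept/placebo for the Double-Blind Period will be administered in Week 23".
- Table 5.1-2, row "Dosing of weekly abatacept/placebo", is marked at Day 141 (Week 20) and not at Day 169 (Week 24).
- Table 5.1-3, row "Dosing of weekly abatacept", is marked at Day 169, which a footnote identifies as the same visit as double-blind Day 169.
- Section 4.5 says that on office-visit days "study medication should be administered AFTER all assessments, including blood draws".
- Section 5.1.1.1 allows 3 days either side of the target day and adds: "Subjects who miss the dose window should skip the SC injection and wait until the next targeted administration day".

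Protocol 3.5 separately requires study drug to be stopped after three or more consecutive, or four or more total, missed doses in the double-blind period.

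**The concern.** The second criterion appears meant to remove subjects who had little or no study drug in the weeks just before the primary assessment. If its threshold exceeds the number of blinded doses in its own window, it cannot do that on blinded doses. It can act only if a dose from the next study period is counted, or if a run that began before the window is counted in full. A programmer building the per-protocol set would have to choose among these readings, and they give different sets. At stake is whether the per-protocol repeat of the primary analysis excludes the subjects it was designed to exclude.

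**Working it through.** **Inputs.** Weekly dosing and last blinded dose in Week 23 (protocol 4.5.1); visit days (Table 5.1-2); thresholds (SAP Appendix 1), where more than 4 means at least 5 and more than 6 means at least 7.

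**Dosing grid.** Target day = 7 × week + 1. This reproduces every post-baseline visit in Table 5.1-2: Week 4 = Day 29, Week 8 = 57, Week 12 = 85, Week 16 = 113, Week 20 = 141, Week 24 = 169. Weeks 0 to 23 give 24 blinded doses, the last on 7 × 23 + 1 = Day 162, consistent with the protocol's Week 23.

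**Blinded doses from Day 141 to Day 169.** Days 141, 148, 155 and 162: four doses, against a requirement of five.

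**Does another reading give a fifth blinded dose?**

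- Exclusive bounds: Days 148, 155 and 162, so three.
- Week 23 read as Days 155 to 161: three.
- Either visit moved by up to 3 days: three or four.
- Dose window: the dose before Day 141 has target Day 134 and can be given no later than 134 + 3 = Day 137. It does not enter the window, and a dose missed beyond its window is skipped.

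The maximum is four. Only adding the open-label Day 169 dose, with inclusive bounds, gives five.

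**Who is excluded?** Take a final run of missed blinded doses ending on Day 162:

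| Run length | Starts | First criterion (7 or more) | Second: blinded doses in window | Second: Day 169 counted, dose taken | Second: Day 169 counted, dose skipped | Second: overlapping run counted in full |
|---|---|---|---|---|---|---|
| 4 | Day 141 | no | no | no | yes | no |
| 5 | Day 134 | no | no | no | yes | yes |
| 6 | Day 127 | no | no | no | yes | yes |
| 7 | Day 120 | yes | no | no | yes | yes |

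A run of four followed by the Day 169 dose is not excluded under any reading. Runs of five or six followed by that dose are excluded only if doses missed before Day 141 count.

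**Scale of one subject.** At the planned rates, rounded to whole subjects, the arms are 45/75 = 60.00% and 25/75 = 33.33%. Removing one subject gives:

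- abatacept: 44/74 = 59.46% (−0.54 points) or 45/74 = 60.81% (+0.81);
- placebo: 24/74 = 32.43% (−0.90) or 25/74 = 33.78% (+0.45).

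This illustrates one exclusion and does not estimate the effect, because the documents give no count of such subjects.

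**The case against.** The strongest reply is that the criterion can be met. Unlike the first, it does not restrict itself to the double-blind period, it ends at Day 169, and Table 5.1-3 schedules a dose that day. That stands as a possible reading, so it would be wrong to call the criterion dead text. But exclusion would then turn on a dose given after the Week 24 assessments, which cannot influence the response being analysed. The words in brackets, abatacept or placebo, also fit poorly with a dose that is abatacept for everyone.

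The second reply is that the affected group is narrow and may be empty. Protocol 3.5 requires stopping well before such a run is complete, and SAP 7.5.2 scores subjects who stop study medication before Week 24 as non-responders. This largely stands. A reader might infer from SAP 7.4.2 that discontinuation is read only from the subject status page, so that every unrecorded case is scored on the observed Day 169 response. The text does not support that. The status-page sentence concerns study periods, whereas the sentence before it defines discontinuation of study medication as stopping without restarting before the study ends. The point is therefore limited to subjects who resume dosing.

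A reader might also infer that Appendix 1 conflicts with SAP 7.2 over Covid-19 deviations. It does not: 7.2 says that the criteria, Covid-19 ones included, are those listed in Appendix 1, and its reference to impact on the primary endpoint matches the definition of a relevant deviation in 6.3. The Covid-19 line simply inherits the same defect.

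Finally, nothing in the documents shows which threshold was intended. That is fair, and it is why the remedy is to reconcile the rule with the schedule.

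**Conclusion.** The point holds as a minor correction. The second missed-dose criterion falls one dose short of being attainable on blinded doses in its window. Whatever reading is adopted, missing all four blinded doses before the primary assessment and resuming at Day 169 does not remove a subject from the per-protocol set under the missed-dose rule.

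This rests on target days fixed at seven-day intervals from Day 1, and on a subject who is not recorded as discontinued, resumes dosing and has no other relevant deviation. The primary ITT analysis and the hierarchical tests of the secondary endpoints are untouched. The number of affected subjects is unknown and may be zero, so the effect on the per-protocol estimate cannot be sized.

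**What to change.** Before unblinding, amend the second missed-dose criterion in SAP Appendix 1 in three respects:

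1. Set the threshold so that missing all four scheduled blinded doses from Day 141 to Day 162 meets it, for example four or more consecutive scheduled double-blind doses.
2. State that the open-label Day 169 dose is not counted.
3. State whether a run that starts before Day 141 is counted in full.

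The Covid-19 missed-dose line then inherits the corrected rule and needs no separate change. This concerns the analysis-set definition only and leaves the stopping rules in protocol 3.5 as they are. The cost is a short wording change and no new data. The per-protocol set may lose a few subjects, or none.
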